CONTACT INFORMATION

For regulatory requirements:	For patient enrollments:	For data submission:

Regulatory documentation must be submitted to the CTSU via the Regulatory Submission Portal.
 
(Sign in at www.ctsuh.org and select the Regulatory > Regulatory Submission.)
 
Institutions with participants waiting that are unable to use the Portal should alert the CTSU Regulatory Office immediately at [name] to receive further instruction and support.
 
Contact the CTSU Regulatory Help Desk at [name] for regulatory assistance.
	
Refer to the patient enrollment section of the protocol for instructions on using the Oncology Patient Enrollment Network (OPEN). OPEN is accessed at https://www.ctsuh.org/OPEN_SYS_TEM/ or https://OPEN.ctsuh.org.
 
Contact the CTSU Help Desk with any OPEN-related questions by phone or email [name], or [contact].
	
Data collection for this study will be done exclusively through Medidata Rave. Refer to the data submission section of the protocol for further instructions.

The most current version of the study protocol and all supporting documents must be downloaded from the protocol-specific page located on the CTSU members' website (https://www.ctsuh.org). Access to the CTSU members' website is managed through the Cancer Therapy and Evaluation Program - Identity and Access Management (CTEP-IAM) registration system and requires log in with a CTEP-IAM username and password.
 
Permission to view and download this protocol and its supporting documents is restricted and is based on person and site roster assignment housed in the CTSU Regulatory Support System (RSS).
		

For clinical questions (i.e., patient eligibility)
 
Contact the protocol team via email at [contact].
 
For clinical data submission questions:
 
AMC Operations and Data Management Center The Emmes Company, LLC [contact] Email: [contact]
		

For non-clinical questions (i.e., unrelated to patient eligibility, treatment, or clinical data submission) Contact the CTSU Help Desk by phone or email:
 
CTSU General Information Line – [name], or [contact]. All calls and correspondence will be triaged to the appropriate CTSU representative.
		

PROTOCOL SYNOPSIS

Title:	Use of a Screening Tool to Describe HIV-Related Cancer Burden and Patient Characteristics in the AIDS Malignancy Consortium
Accrual Target:	A minimum of 360 and maximum of 720 participants
Regulatory Status:	Non-Interventional
Population:	Participants with a dual diagnosis of both cancer (current or diagnosed within 5 years) and underlying HIV infection, who present for care at AMC domestic sites.
Regimen:	Participants will be identified via screening of electronic medical records or institutional databases. All eligible participants will have one visit for the collection of broad demographic and clinical data. Participants initiating or receiving ongoing treatment for their cancer will attend a single follow-up visit. Data collection at study visits will occur via survey procedures and/or medical record review.
Anticipated Trial Duration:	Approximately 3 years for accrual and follow-up
Primary Objective:	To estimate the number of cancers in people with HIV (PWH) who present for care at domestic AMC sites
Secondary Objectives:	To characterize participants that are eligible but not enrolled onto AMC clinical trials to understand site-specific and trial-specific accrual barriers
Exploratory Objectives:	
1. To standardize and expand the quantity and quality of sociodemographic and cancer diagnostic and treatment characteristics collected for PWH receiving care at domestic AMC sites.2. To describe cancer patient health-related QOL for PWH at domestic AMC sites using validated tools: European Organization for Research and Treatment of Cancer Quality of Life Questionnaire [EORTC QLQ-C30] and Supportive Care Needs Survey Short Form 34 [SCNS-SF34].

PROTOCOL SCHEMA

LIST OF ABBREVIATIONS

AE	Adverse event
AIDS	Acquired immunodeficiency syndrome
AMC	AIDS Malignancy Consortium
ART	Antiretroviral therapy
CBC	Complete blood count
CDC	Centers for Disease Control and Prevention
CDUS	Clinical Data Update System
CRF	Case report form
CTEP	Cancer Therapy Evaluation Program
CTEP-AERS	Cancer Therapy Evaluation Program Adverse Event Reporting System
DSMB	Data and Safety Monitoring Board
ECOG	Eastern Cooperative Oncology Group
EORTC-QLQ	European Organization for Research and Treatment of Cancer Quality of Life Questionnaire
FDA	Food and Drug Administration
HIV	Human immunodeficiency virus
HPV	Human papillomavirus
IRB	Institutional review board
IND	Investigational new drug
NCI	National Cancer Institute
ODMC	Operations and data management center
PWH	People with HIV
POSEC	Patient Outcomes, Survivorship, and Engagement Committee
PrEP	Pre-exposure Prophylaxis
PROs	Patient-Reported Outcomes
QOL	Quality of Life
RNA	Ribonucleic acid
SAE	Serious adverse event
SCNS-SF34	Supportive Care Needs Survey Short Form 34
SES	Socioeconomic Status

1.0 OBJECTIVES

1.1 Primary Objective

To estimate the number of cancers in PWH who present for care at domestic AMC sites

1.2 Secondary Objectives

1.2.1 To characterize participants that are eligible but not enrolled onto AMC trials to understand site-specific and trial-specific accrual barriers, particularly for minority and underserved populations.

1.3 Exploratory Objectives

1.3.1 To standardize and expand the quantity and quality of sociodemographic (e.g., racial/ethnic distribution, SES), HIV-related [e.g., Antiretroviral Therapy (ART) medications, co-morbidities], and cancer diagnostic and treatment characteristics collected for PWH receiving care at domestic AMC sites.

1.3.2 To describe cancer patient health-related Quality of Life (QOL) for PWH at domestic AMC sites using validated tools: European Organization for Research and Treatment of Cancer Quality of Life Questionnaire [EORTC QLQ-C30] and Supportive Care Needs Survey Short Form 34 [SCNS-SF34].

2.0 BACKGROUND

2.1 Introduction

Accrual of adults onto cancer clinical trials is challenging, and the cancer burden in the U.S. HIV population is growing to include a broader spectrum of both AIDS-defining and age-related, non-AIDS-defining cancers [1]. The objective of this protocol is to collect high-quality data that will address both trends.

Fewer than 5% of U.S. adult cancer patients, and even fewer affected by both cancer and HIV/AIDS, enroll onto clinical trials. Research groups and government-sponsored organizations increasingly have focused on engaging communities to participate in cancer clinical trials. To broaden the understanding of characteristics of adults screened for, and those opting out of, NCI-sponsored cancer clinical trials, NCI Community Oncology Research Program (NCORP) developed a clinical trials screening tool (NCORP DCP-001). AIDS Malignancy Consortium (AMC) clinical trials share similar challenges to the NCI trials described in NCORP DCP-001 [2], so screening tools to identify consistent barriers to participation for people living with HIV (PWH), who have historically been under-represented in clinical trials, are urgently needed across the AMC. The AMC preliminarily examined patient-level characteristics and perceptions that influenced decision-making about trial participation for 67 patients diagnosed with anal cancer or high-grade anal intraepithelial neoplasia [3]. Of those 67 participants, most were male (92.5%) non-Hispanic white (89.5%) adults (48.3 years old on average); most learned about AMC clinical trials from a medical provider (98.5%); and most (73.1%) expressed little general knowledge about clinical trials. Participants recommended system-level changes to accelerate patient access to clinical trials. Participants further underscored the need to address knowledge barriers to clinical trial participation. This protocol will follow-up on these recommendations by proposing an AMC effort across all domestic sites to identify patient demographic (e.g., race/ethnicity), socioeconomic (e.g., homelessness/insurance status), and cancer-related (e.g., extent of disease) features associated with AMC clinical trial participation. This approach represents a large expansion beyond those preliminary data published from AMC-S006 by allowing enrollment across all domestic AMC sites, including all cancer types and AMC scientific working groups in data collection, and obtaining valuable information from not only participants who choose to enroll but, perhaps more importantly, from participants who present to AMC sites and are eligible for an open trial but who opt out of participation.

In 2019, the AMC implemented a screening and prospective observational cohort protocol in Latin America (AMC-S008), with the goal of estimating the number of HIV-associated cancers of various types presenting at participating AMC clinical sites in the region. That protocol captures broad demographic and clinical data to generate further clinical treatment outcome hypotheses and research questions within the AMC international portfolio. The effort proposed here would represent the first such protocol focused on uniform prospective cancer patient data collection across AMC domestic sites.

In summary, this protocol will implement a screening tool at domestic AMC sites that will capture cancer patterns in PWH, as well as broad demographic, cancer/clinical, and quality

of life (QOL) data from participants to generate future research questions and design efforts to improve AMC clinical trial participation.

2.2 Study Design and Rationale

Rationale: Collection of expanded patient demographics and clinical information to include socioeconomic status (SES), method of diagnoses, and engagement in recommended oncology care is one way to enhance our ability to evaluate both the full patient population served at AMC domestic sites and to identify factors influencing participation in AMC clinical trials. This includes features of both participants who are potentially eligible but elect not to screen for trials and participants who are screened but deemed ineligible. Understanding characteristics of those presenting for care at AMC sites is critical to inform the design of future AMC cancer prevention and treatment efforts and assessment of feasibility of proposed trials to make informed decisions for resource allocation. In addition, this information will be invaluable in informing survivorship programs for PWH and cancer.

Capturing patient health-related quality of life (QOL) experiences via patient-reported outcomes (PROs), is essential; thus, in 2020 the AMC formed the Patient Outcomes, Survivorship, and Engagement Committee (POSEC) to ensure that this data is documented in AMC trials using validated, culturally appropriate PRO tools that are of minimal burden to trial participants. Accordingly, this protocol will include an optional, brief PRO/QOL needs assessment that will allow for a better understanding of whether participant PRO/QOL features are potential barriers to clinical trial enrollment. This will serve as the first widespread use of QOL data across the AMC, both fulfilling the mission of POSEC and building a foundation for future, longitudinal survivorship efforts led by POSEC in the AMC.

In summary, anticipated outcomes of this observational protocol are as follows:

- Identify patient and clinical features associated with AMC clinical trial participation
- Capture a complete picture of cancer burden in PWH at domestic AMC sites to guide future clinical trial priorities
- Establish a robust population science framework for high-quality data collection across AMC sites
- Serve as the first protocol to build a foundation for future QOL-based and survivorship efforts across the domestic AMC

Study Design: All PWH who present for care at participating AMC clinical trial sites with a diagnosis of cancer will be tracked on a screening list. Institutional review board (IRB) approvals will be obtained to allow screening of the electronic medical record or institutional databases to identify these participants, as well as approach them after identification for further data collection. After identification, eligible patients will be approached to provide consent and participate in the collection of broad demographic and clinical data. To facilitate patient recruitment, and due to the on-going COVID-19 pandemic, remote consenting prior to further data collection will be allowed, within the guidelines provided by the NCI Central Institutional Review Board (NCI CIRB) policies (see <https://www.ncicirb.org/announcements/remote-consent-procedures-revised-faqs->

due-covid-19). Such communications will be done via HIPAA-compliant methods such as telephone, personal delivery of documents, US postal service, REDCap, or other compliant electronic platform. The remote consent process will parallel the consent processed used for in-person consenting. The only difference will be the method(s) of communication and optional use of eSignatures, only if implemented according to NCI CIRB SOP section 2.3.1.6. The study team will ensure that, as with in-person consenting, the participant is given sufficient opportunity to ask questions, is able to understand the nature of this study and what participation entails, and is provided a copy of the final, completed consent signed by all parties involved.

This trial is a one visit study for those with history of malignancy diagnosed in the past 5 years, including those with cancer currently in remission. There will be one follow-up visit for those initiating or receiving on-going treatment for their cancer. In all participants who consent to participate, data captured will include the following:

Table 2-A: Model data collection

Participant Characteristics	Date of birth, biological sex, gender identity, race, ethnicity, height and weight
Sociodemographic	Socioeconomic status (e.g., ZIP code, housing status [homeless y/n]), health insurance (insured/uninsured, type if insured)
Health Behaviors	Tobacco use (type, exposure [pack/day, years use]), illicit drug use (ever, type, years exposure), alcohol use (ever, exposure [drinks/week], years exposure)
Comorbid Conditions	Hepatitis B and C co-infection, cardiovascular disease (y/n, type), psychiatric conditions (y/n, type), non-cancer pulmonary conditions (y/n, type), hepatic dysfunction, hematologic abnormalities, renal dysfunction, neurologic disorders, endocrine disorders (including thyroid disorders, and diabetes)
HIV Care	Current ART regimen, years of ART use, year of HIV diagnosis, history of opportunistic infections, recent HIV viral load and CD4+ T-cell count
Status of Cancer Diagnosis	New, primary or recurrent disease; current metastatic or locally advanced, inoperable cancer; history of malignancy diagnosed within 5 years / cancer currently in remission
Cancer Details	Cancer type, date cancer diagnosed, diagnosis methods (clinical, cytology, histology), pathology performed, date of pathology, staging, staging methods (clinical, radiographic, surgical), current ECOG Performance Status (PS), current laboratory (CBC) values, cancer treatment history (for metastatic tumors or disease in remission)
Cancer Treatment Plan	Planned treatment (e.g., chemotherapy versus radiation versus surgery versus antiretroviral therapy [ART] only versus best supportive care/watchful waiting), location of planned treatment, timeline of planned treatment (start date), if past diagnosis and treatment- end date, enrollment in clinical trial, and clinical trial details

Quality of Life/Survivorship	European Organization for Research and Treatment of Cancer Quality of Life Questionnaire (EORTC QLQ-C30: Global health status, physical functioning, role functioning, emotional functioning, cognitive functioning, social functioning, fatigue, nausea and vomiting, pain, dyspnea, insomnia, appetite loss, constipation, diarrhea, financial toxicity) and Supportive Care Needs Survey Short Form 34 (SCNS-SF34: psychological needs, health system and information needs, physical and daily living needs, patient care and support needs, sexuality needs)
------------------------------	---

For participants initiating therapy or currently under treatment, a short interval follow-up (12 weeks \pm 2 weeks), will be used to ascertain vital status, state of planned cancer therapy (initiated as planned versus delayed initiation, no initiation, or initiation of alternate therapy instead of planned therapy) and any reasons for therapy not being initiated as planned (e.g., comorbidity, cancer progression, patient preference, insurance denial), and optional quality of life changes between initial registration and this short interval follow-up. An approximate 12-week follow-up assessment is expected to coincide with planned treatments/clinical follow-up and therefore minimize unnecessary clinic visits that could increase patient burden. The data collected at this later time point will be limited, as the intent capture is to ascertain the relationship between planned therapy and therapy received, as well as any QOL changes that coincide with start of therapy and/or clinical trial enrollment.

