3.1 Eligibility Criteria

_____ 3.1.1 Participant can understand and is willing to sign a written informed consent document.

_____ 3.1.2 HIV positive. Documentation of HIV-1 infection by means of any one of the following:

- Documentation of an HIV diagnosis in the medical record by a licensed health care provider;
- Documentation of receipt of antiretroviral therapy (ART) (i.e., at least two different medications that do not constitute a prescription for pre-exposure prophylaxis [PrEP]) by a licensed health care provider. Documentation may be a record of an ART prescription in the medical record, a written prescription in the name of the participant for ART, or pill bottles for ART with a label showing the participant's name;
- HIV-1 RNA detection by a licensed HIV-1 RNA assay demonstrating >1000 RNA copies/mL;
- Any licensed HIV screening antibody and/or HIV antibody/antigen combination assay confirmed by a second licensed HIV assay such as a HIV-1 Western blot confirmation or HIV rapid multispot antibody differentiation assay.

Note: The term "licensed" refers to a kit that has been certified or licensed by an oversight body within the participating country and validated internally (e.g., U.S. FDA).

WHO (World Health Organization) and CDC (Centers for Disease Control and Prevention) guidelines mandate that confirmation of the initial test result must use a test that is different from the one used for the initial assessment. A reactive initial

rapid test should be confirmed by either another type of rapid assay, or an E/CIA that is based on a different antigen preparation and/or different test principle (e.g., indirect versus competitive), a Western blot, or a plasma HIV-1 RNA viral load.

- _____ 3.1.3 Patient was diagnosed with or treated for cancer within the last 5 years. Participants will qualify under one of three categories:
- New, primary or recurrent diagnosis –Considering or currently receiving cancer treatment
 - Metastatic or locally advanced cancer – This includes cases for which there are no current definitive therapy options for cure (i.e., inoperable) but may be considered for non-standard / non-curative therapies.
 - Prior diagnosis (within 5 years), in remission – Not currently on cancer treatment other than ART or maintenance therapy.
- _____ 3.1.4 Age \geq 18 years.
- _____ 3.1.5 Participant presents to an AMC domestic clinical trial site for either clinical care or research.

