8.2 Enrollment Data Collection

Following informed consent, additional, identifiable data will be collected, including:

- 8.2.1 Patient characteristics: Date of birth, biological sex, gender identity, race, ethnicity, height and weight
- 8.2.2 Sociodemographic: Socioeconomic status (e.g., ZIP code, housing status [homeless y/n, categories for frequency of housing insecurity]), health insurance (insured/uninsured, type if insured)
- 8.2.3 Health behaviors: Tobacco use (type, exposure [pack/day, years use]), illicit drug use (ever, type, years exposure), alcohol use (ever, exposure [drinks/week], years exposure)
- 8.2.4 Comorbid conditions: Hepatitis B and C co-infection, cardiovascular disease (y/n, type), psychiatric conditions (y/n, type), non-cancer pulmonary conditions (y/n, type), hepatic dysfunction, hematologic abnormalities, renal dysfunction, neurologic disorders, endocrine disorders (including thyroid disorders, and diabetes)
- 8.2.5 HIV care: Current ART regimen, years of ART use, year of HIV diagnosis, history of opportunistic infections, most recent HIV viral load and CD4+T-cell count relative to participant visit).

8.2.6 Status of cancer diagnosis (one of the following):

- New diagnosis, pre-treatment phase
- New diagnosis, treatment phase
- Prior diagnosis, in remission (within 5 years of initial diagnosis or treatment)
- Prior diagnosis, recurrent, pre-treatment phase
- Prior diagnosis, recurrent, treatment phase
- Prior diagnosis, recurrent, no treatment planned

8.2.7 For participants with a new diagnosis (pre-treatment or treatment), the following will be collected:

- Cancer type, date of cancer diagnosis, method of diagnosis (clinical, cytology, histology), type of pathology performed (Hematoxylin and Eosin, immunohistochemistry, other), date of pathology, staging, staging methods (clinical, radiographic, surgical), date(s) of staging, current ECOG Performance Status (PS), current laboratory values (this would include complete blood count, renal and liver function, electrolytes)
- Cancer treatment plan: Detailed planned or current treatment. This should encompass surgical interventions, radiotherapy, and chemotherapy (agent names), including dates of planned or current therapy, and whether cancer care is being received or will occur at the enrolling institution.

8.2.8 For participants with a prior diagnosis in remission, the following will be collected:

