9.0 MEASUREMENT OF EFFECT

This is a non-interventional protocol.

The following definitions will be employed for case classification and data reporting for the primary protocol objective, to estimate the number of cancers in PWH who present for care at domestic AMC sites:

Table 9-A: Definitions for case classification and data reporting

Site-specific frequency of primary cancer cases	Total number of participants that present to the site with a first diagnosis of cancer. This encompasses cases that are in the period from histologically proven cancer to initiation of planned first-line therapy, as well as cases already receiving the planned first-line therapy for primary disease.
Site-specific frequency of recurrent cancer cases	Total number of participants that present to the site with a diagnosis of cancer within the last 5 years. This includes participants on surveillance, or best supportive care.
Site-specific frequency of prior cancer cases	Total number of participants that present to the site with a recurrent (i.e., non-primary) cancer diagnosis. This encompasses cases that are pre-treatment for recurrent disease, undergoing planned non-first-line therapy, or cases for whom no anti-cancer therapy is planned, including due to metastatic or locally advanced, inoperable disease.
Pre-treatment phase	The period in which a participant has a histologically diagnosed cancer, with cancer-specific treatment planned but not yet initiated.
Treatment phase	The period in which the participant has started therapy for cancer. This can include surgery, radiation, and/or chemotherapy. This period completes when all planned therapy has been completed within a therapeutic encounter.
First-line therapy	All therapy performed as part of a treatment plan with a new/primary diagnosis of cancer, including surgery, radiotherapy, and chemotherapy, alone or in combination.
No treatment planned	The point at which no further active cancer treatments are planned. Initiation of best supportive care or palliative care.

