EORTC QLQ-C30 subscale and overall scores will be used to describe participant symptom and health-related quality of life burden. SNSCS-SF34 scores will be used to categorize participants based on the degree to which their needs are met. Baseline EORTC QLQ-C30 and SCNS-SF34 scores will also be compared according to successful enrollment versus not using t-test or Wilcoxon rank sum tests depending on distribution of scores. These data may describe enrollment barriers previously unknown. For example, comorbidity burden, prior cancer treatment history, or self-reported quality of life at initial cancer presentation may be risk factors for elective participation. These analyses will provide preliminary data to inform evidence-based interventions aimed at increasing clinical trials participation among PWH at domestic AMC sites. To address minority and underserved populations, additional analyses will examine the interaction with race, ethnicity, socioeconomic status, and health insurance status to compare participant characteristics according to groups defined by enrollment status and these variables. Similarly, interactions with age, cancer type, treatment, and time since diagnosis will be investigated. Finally, these analyses will inform a multivariable logistic model that predicts successful trial outcome that includes dependent variables for participant characteristics; interactions with indicators of minority, socioeconomic status, and health insurance will be investigated in this model as well as with age, cancer type, treatment and time since diagnosis.

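### Section 8.2.6 has no status for advanced cancer that never remitted, so such cases past first-line therapy must be entered as recurrent or as new

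*Combined protocol and SAP*

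**What the plan says.** Section 2.2, Table 2-A, gives the status of the cancer diagnosis in three groups: "New, primary or recurrent disease; current metastatic or locally advanced, inoperable cancer; history of malignancy diagnosed within 5 years / cancer currently in remission". The second of these, "current metastatic or locally advanced, inoperable cancer", stands as a group of its own. In the same table, the Cancer Details row promises "cancer treatment history (for metastatic tumors or disease in remission", with no restriction to recurrent cases.

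Criterion 3.1.3 has the same structure: "Participants will qualify under one of three categories". The second category is metastatic or locally advanced cancer, including cases with no definitive curative option "but may be considered for non-standard / non-curative therapies".

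Section 8.2.6 requires one choice from six: new diagnosis in the pre-treatment or treatment phase; prior diagnosis in remission; and prior diagnosis, recurrent, in three phases, for example "Prior diagnosis, recurrent, treatment phase". The choice decides which items follow: 8.2.7 for new, 8.2.8 for remission, 8.2.9 for recurrent.

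Table 9-A in section 9.0 defines the groups reported for the primary objective. Primary cases run from histological proof through planned first-line therapy. The definition of a recurrent, non-primary diagnosis takes in later-line therapy and "cases for whom no anti-cancer therapy is planned, including due to metastatic or locally advanced, inoperable disease".

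Section 10.3 says that "comorbidity burden, prior cancer treatment history, or self-reported quality of life at initial cancer presentation may be risk factors" for whether a patient takes part in a trial.

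**The concern.** The planned data and the eligibility rule recognize advanced disease as a distinct state, but the field that sites fill in does not. Take a patient whose cancer was metastatic at diagnosis two years ago, never went into remission, and is now on a later line of therapy. The patient is eligible, but the diagnosis is no longer new and there has been no remission from which to recur.

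Two things are at stake. Section 10.1.2 estimates new and existing cases per month, and Table 9-A reports primary, recurrent and prior cases by site. If sites resolve the same patient differently, those splits are not comparable between sites. In addition, treatment history, which section 10.3 wants to examine as an enrollment barrier, would be missing for pretreated patients entered as new.

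**Working it through.** No sample-size or power figure is involved, so the check sets the passages side by side.

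| Place | Groups | Separate group for advanced disease? | Prior treatment collected? |
|---|---|---|---|
| Table 2-A | 3 | Yes | Promised for metastatic tumors and for remission |
| 3.1.3 | 3 | Yes | Not addressed |
| 8.2.6, new (8.2.7) | 2 of 6 | No | No; planned or current treatment only |
| 8.2.6, remission (8.2.8) | 1 of 6 | No | Yes |
| 8.2.6, recurrent (8.2.9) | 3 of 6 | No | Yes |

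Prior treatment is thus collected under 1 + 3 = 4 of the 6 statuses and not under the 2 new ones.

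**The example patient.** Remission is excluded, which leaves two paths.

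1. *Recurrent.* Table 9-A ends the primary group with first-line therapy and names later-line therapy under the non-primary definition, so its text points here. Section 8.2.9 then collects the initial diagnosis and prior treatment, and no history is lost. The cost is that never-remitted first cancers are counted together with true recurrences and cannot be separated by status.
2. *New.* An existing case is counted as new. Section 8.2.7 has no prior-treatment item, so the Table 2-A promise is not met.

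**Does Table 9-A decide between the paths?** Not reliably. The row labelled recurrent holds participants diagnosed within five years, including those on surveillance. The row labelled prior holds the recurrent, non-primary definition. The two labels appear interchanged. Section 8.2.6 does not refer to the table.

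**First diagnosis with no treatment planned.** In 8.2.6 a no-treatment option exists only for recurrent disease, and 8.2.9 is the only section that asks why no therapy is planned. Criterion 3.1.3 nevertheless admits advanced cases without curative options, and a first diagnosis among them may have no treatment planned.

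**Overlap in 3.1.3.** A newly diagnosed metastatic case considering treatment fits both the first and the second category, so the eligibility category does not reliably identify advanced disease either.

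**What is not affected.** The intervals in Table 10-A follow from p ± (1.96 × √(p(1 − p)/n) + 1/(2n)). For p = 0.493:

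- n = 360: 1.96 × 0.02635 + 0.00139 = 0.0530, giving 44.0% to 54.6%, as stated.
- n = 720: 1.96 × 0.01863 + 0.00069 = 0.0372, giving 45.6% to 53.0%, as stated.

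Only the cancer-type share and n enter. Disease status does not, so neither this precision nor the cancer-type percentages change.

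**The case against.** The strongest reply is that Table 9-A already assigns these patients. It excludes them from primary, and by equating recurrent with non-primary it uses the word broadly. A site that follows it uses 8.2.9 and collects everything needed. This stands in part: it gives the likelier path, and it means that treatment history is lost only when a case is entered as new. It does not close the gap, because of the row labels and the missing cross-reference, and because following the table still merges persistent with recurrent disease.

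Other replies have some force:

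- Appendix I lists prior and/or current treatment at enrollment for everyone, but its footnote defers to section 8.2 for the specific records.
- Date of diagnosis and staging are collected under 8.2.7, so an old cancer entered as new could be found and reclassified. Prior lines of therapy and current inoperability would not be recovered that way.
- The section 10.3 eligibility check for active disease uses diagnosis with stage and histology, age and indication, not the 8.2.6 status, so that denominator is not directly affected.
- The form instructions and data entry guide named in section 11.2 may settle the coding. They are not part of these documents.

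A reader might infer that advanced cases in general lose their treatment history, that those affected are the most heavily treated patients, or that the recurrent count is inflated by some large percentage. The documents support none of these. The loss is confined to the new path, nothing describes treatment intensity, and neither the share of never-remitted cases nor the share of recurrences is given.

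**Conclusion.** The point holds as a mismatch between the planned categories and the status field. Persistent advanced disease past first-line therapy has no accurate entry in 8.2.6, and neither does a first diagnosis with no treatment planned. The consequence is misclassification on either path, plus missing prior treatment on the new path only.

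The number of participants affected cannot be derived, and no inflation percentage should be quoted. The conclusion assumes that the eCRF follows 8.2.6 to 8.2.9 as written and that no separate coding instruction resolves the case. It bears on the classification used for the primary objective and on the completeness of one candidate barrier in section 10.3, not on sample size or on the cancer-type results. It should be corrected, because history not abstracted at the enrollment visit would need later re-abstraction.

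**What to change.** - Add to 8.2.6 a status for a prior diagnosis that is persistent or progressive and was never in remission, with pre-treatment, treatment and no-treatment-planned phases. Route it to the 8.2.9 items.
- Add to 8.2.6 a new diagnosis with no treatment planned.
- Record metastatic/locally advanced as a yes/no field for all participants, and collect prior treatment for every metastatic case whatever its status.
- Reconcile Table 9-A with these statuses, check and correct its recurrent and prior row labels, and refer to it from 8.2.6. Tabulate persistent cases separately from recurrent ones.

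The cost is a few eCRF fields and a protocol amendment with CTEP and CIRB approval (section 12.2). No patients or visits are added.
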